No prior clinical experience with RO7239958 exists. In Study NP40520 healthy participants and CHB patients will be kept under medical observation and monitored closely for clinical and laboratory adverse events. CHB patients eligible to join study NP40520 will be established on effective NUC therapy, have preserved hepatic function, and have no current or past history of cirrhosis, thus reducing the risk of liver-related adverse events. The evaluation of the potential risks of treatment, and the specific tests, observations, and precautions required for clinical studies with RO7239958 are based on information obtained preclinically from 2-week and 4-week studies in rats and NHPs, and a 39-week exploratory study in NHPs. In addition, there is prior experience with other LNA SSOs, such as that derived from study BP39405 (a two-part randomized SAD/multiple ascending dose study to evaluate RO7062931 in healthy volunteers and CHB patients).

[REDACTED]

A reduction of expression levels for a certain subset of host transcripts could not be detected ([Lim et al 2018](#)).

[REDACTED]

[REDACTED]

[REDACTED]

RO7239958 will be administered in a hospital or clinic environment under supervision of an experienced clinician. Detailed instructions on dosage and administration of RO7239958 are provided. SC administration of LNA SSOs carries a risk of injection-site reactions (ISRs). At higher doses, there is also a potential risk for LNA SSO-related liver and kidney toxicity ([Chen et al 2015](#); [van Poelgeest et al 2015](#)). Furthermore, it is hypothesized that HBsAg suppression may potentially contribute to restoring HBV-specific immunity in CHB patients, which may result in a transaminase flare. Frequent monitoring of full blood count, clotting, serum biochemistry and urinalysis will be performed during the course of the study, and close monitoring of renal and hepatic safety parameters will be included, comprising testing for renal function, urine sediment, serum transaminases, and hepatic synthetic and secretory function. Defined stopping criteria are proposed for dosing of individual study participants, cohorts and arms. In addition to standard measures of renal and liver safety, exploratory markers of renal and liver injury will be analyzed in urine and blood samples, respectively. Safety monitoring will be extended post-dosing for 12 weeks in both healthy participants and CHB patients.

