4.1.3 Stopping Rules Criteria

Liver-related

Isolated elevations in liver transaminases (ALT or AST) in the absence of liver function abnormalities may occur after administration of RO7239958 as a recognized LNA SSO class effect. In addition to the LNA SSO class effect, CHB patients may also hypothetically experience transaminase flares if HBsAg suppression leads to immune-restoration. Stopping criteria have been developed to take these potential effects into account.

Part 1: If, at a given dose level, one or more of the criteria described below is fulfilled, dose-escalation to the next cohort will be paused in order to assess the possible underlying causes and relation to RO7239958. If a relation to study treatment cannot be excluded by the Investigator and the Sponsor's Medical Monitor, dose escalation will be halted.

Criteria:

- At least two of eight healthy participants receiving RO7239958 experience dose-limiting AEs (DLAEs) of an ALT or AST increase $> 5x$ the upper limit of normal (ULN; confirmed by retesting within 48 hours) with preserved measures of liver function (total bilirubin, and INR or prothrombin time [PT]),

or

- At least one of eight healthy participants receiving RO7239958 experiences one of the following DLAEs: confirmed (within 48 hours) increase in ALT or AST $> 3x$ ULN accompanied by confirmed total bilirubin $> 2x$ ULN, INR > 1.5 , or PT $\geq 1.5x$ ULN, or appearance of jaundice or symptoms suggestive of drug-induced liver injury (e.g., fatigue, nausea, vomiting, right upper quadrant abdominal pain or tenderness, fever, rash, and eosinophilia).

Part 2: If, at a given dose level and/or regimen, one or more of the criteria described below is fulfilled, dosing in a patient and in a given arm, and any dose escalation, will be paused in order to assess the possible underlying causes and relation to RO7239958. If a relation to study treatment cannot be excluded by the Investigator and Sponsor's Medical Monitor, dosing and any potential dose escalation will be halted.

Criteria:

- At least two of six patients receiving RO7239958 experience a DLAE of an ALT or AST increase of > 8-fold relative to the baseline value (defined as the average values of the two measurements taken within the screening period), confirmed by retesting within 48 hours, with preserved measures of liver function (total bilirubin and INR or PT),
or

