- At least one of six patients receiving RO7239958 experiences one of the following DLAEs: confirmed (within 48 hours) increase in ALT or AST > 3-fold the baseline value, accompanied by confirmed total bilirubin > 2x ULN, INR > 1.5, or PT \geq 1.5x ULN, or appearance of jaundice or symptoms suggestive of drug-induced liver injury (e.g., fatigue, nausea, vomiting, right upper quadrant abdominal pain or tenderness, fever, rash, and eosinophilia).

Repeat dosing of a participant within an arm will be delayed if the participant receiving RO7239958 experiences an ALT or AST increase > 5-fold and \leq 8-fold relative to the baseline value, confirmed by retesting within 48 hours, with preserved measures of liver function (total bilirubin and INR or PT). Dosing may resume when the ALT or AST levels return to \leq 5-fold the baseline value.

Other stopping criteria

All Parts: Dosing and dose-escalation in healthy participants in Part 1 and dosing for a patient and a treatment arm and any potential dose escalation in Part 2 will not be implemented as planned if one of the criteria described below is fulfilled, unless it is apparent to the Investigator and the Sponsor that the occurrence is not related to RO7239958.

Criteria: At least two of eight healthy participants or at least two of six CHB patients receiving RO7239958 experience one or more of the following DLAEs:

- Confirmed decline in eGFR < 60 ml/min
- Grade 3 or 4, or otherwise significant (as defined by the Investigator) RO7239958-related AEs of the same character, or Grade 3 or 4 laboratory abnormalities.
- Other findings (regardless of the incidence rates) that at the joint discretion of the Sponsor and the Investigator indicate that dosing and any dose escalation should be halted (see Section 7.1).

General considerations

Part 1: In case dose-escalation is stopped, lower doses within the tolerated dose-range could be investigated or a previous dose could be repeated in subsequent cohorts, by mutual agreement between the Sponsor and Investigator, in order to increase the amount of data within the tolerated dose-range.

Part 2: In case an arm is stopped, alternative regimens within a previously tolerated dose/exposure range could be further investigated, or a previous regimen could be repeated in subsequent arms, by mutual agreement between the Sponsor and Investigator, in order to increase the amount of data within the tolerated dose/exposure range.

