4.1.4 Communication Strategy

Information will be communicated, as follows:

- The Investigator must confirm to the Sponsor that a participant has been dosed and provide a brief summary of the status of the participant in terms of safety and tolerability to RO7239958 or placebo, communicated by email or telephone.
- In Part 1, the Investigator will provide a safety assessment feedback to the Sponsor of the first two sentinel-dosed healthy participants of each cohort before proceeding to dosing the remaining participants.
- For all parts of the study and in the event of a dose-limiting adverse event (DLAE), the Investigator will contact the Sponsor immediately to discuss participant status and action taken or to be taken.
- After completion of each cohort in Part 1 (i.e., after the last participant in the cohort has reached the last day of the evaluation period, comprising 21 days of monitoring plus a further 7 days of clinical observation, for a total of 28 days), the Sponsor will organize a teleconference with the Investigators to discuss the safety and tolerability of RO7239958 or placebo, and to discuss the dose for the next cohort.

During each teleconference:

- Safety and tolerability (see [Appendix 2](#)) will be discussed along with the results of available PK data, in addition to safety laboratory results and any other available data that may assist the decision process.
- Dose escalation will only proceed if the Investigator and the Sponsor are satisfied with the safety profile of the previous cohort and agree to escalate to the next dose level.
- The decision of these meetings will be documented in writing and both the Sponsor and Investigator will approve the minutes of these meetings to confirm agreement.

For Part 2, a teleconference will be organized to discuss accumulated data from Arms 1 and 2 in Part 2a prior to the start of Arms 3 and 4; a teleconference will also be organized as above after completion of Arms 3 and 4 (*and optional Arm 5*) and before the start of subsequent arms in Part 2b if applicable.

In addition to these communications, the Sponsor and investigators will be in regular contact throughout the study by email or telephone, as per normal interactions during the conduct of a clinical study, and the Sponsor will arrange regular teleconferences and meetings to discuss study status.

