7.1 DISCONTINUATION OF STUDY TREATMENT

See the SoA (Section 1.3) for data to be collected at the time of treatment discontinuation and follow-up and for any further evaluations that need to be completed.

Participant must discontinue study treatment if they experience any of the following:

- Participant withdrawal of consent at any time.
- Any medical condition that the Investigator or Sponsor determines may jeopardize the participant's safety if he or she continues in the study.
- Investigator or Sponsor determines it is in the best interest of the participant.
- Pregnancy
- If stopping criteria are met (see Section 4.1.3)
- If non-compliance with study requirements as judged by the Investigator and consultation with the Sponsor.

Participants who discontinue study treatment prematurely will be asked to return to the clinic for a study completion/early termination visit (see Section 1.3) and may undergo follow-up assessments (see Section 1.3). The primary reason for premature study treatment discontinuation should be documented on the appropriate eCRF. Participants who discontinue study treatment prematurely can be replaced in both Parts 1 and 2.

Discontinuation of study intervention for abnormal liver function should be considered by the Investigator when a participant meets one of the conditions outlined in Section 6 of Appendix 3 or if the Investigator believes that it is in best interest of the participant.

If a clinically significant finding is identified (including, but not limited to changes from baseline in QT interval corrected using Fridericia's formula [QTcF]) after enrollment, the investigator or qualified designee will determine if the participant can continue in the study and if any change in participant management is needed. This review of the ECG taken at the time of collection must be documented. Any new clinically relevant finding should be reported as an AE.

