8.3.6 Non-Serious Adverse Events of Special Interest

Non-serious adverse events of special interest (NSAESI) are required to be reported by the Investigator to the Sponsor immediately (i.e., no more than 24 hours after learning of the event; see [Appendix 2](#) for reporting instructions).

NSAESI for this study include the following:

- Dose-dependent gastrointestinal disorders (including nausea, vomiting and diarrhea).
- Confirmed ALT or AST > 5x ULN (in healthy participants) or > 8x baseline (in CHB patients).
- Confirmed ALT or AST > 3x ULN (in healthy participants) or > 3x baseline (in CHB patients) accompanied with increased total bilirubin > 2x ULN (or clinical jaundice).
- Confirmed ALT or AST > 3x baseline (in CHB patients) accompanied with INR > 1.5 (or PT ≥ 1.5 ULN).
- Confirmed ALT or AST >3x baseline (in CHB patients) with the appearance of fatigue, nausea, vomiting, right upper quadrant abdominal pain or tenderness. fever, rash, and eosinophilia

- Suspected transmission of an infectious agent by the study treatment, as defined below:

Any organism, virus, or infectious particle (e.g., prion protein transmitting transmissible spongiform encephalopathy), pathogenic or non-pathogenic, is considered an infectious agent. A transmission of an infectious agent may be suspected from clinical symptoms or laboratory findings that indicate an infection in a patient exposed to a medicinal product. This term applies only when a contamination of the study treatment is suspected.

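### Part 2 liver rules require an individual dosing delay for confirmed isolated ALT/AST above 5-fold and up to 8-fold baseline, but set no explicit hold for a single patient first confirmed above 8-fold

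*Combined protocol and SAP*

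**What the plan says.** Section 4.1.3 (Part 2) grades isolated transaminase rises against each patient's baseline, which is the mean of two screening-period values.

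- **Individual delay.** "Repeat dosing of a participant within an arm will be delayed if the participant receiving RO7239958 experiences an ALT or AST increase > 5-fold". The sentence goes on to set an upper limit of 8-fold, inclusive, and asks for confirmation within 48 hours and preserved bilirubin and INR or PT. "Dosing may resume when the ALT or AST levels return to" 5-fold baseline or lower.
- **Isolated rise above 8-fold.** The criterion is "At least two of six patients receiving RO7239958 experience a DLAE of an ALT or AST increase of > 8-fold relative to the baseline" value. The pause of dosing in the patient and in the arm follows only once a criterion is fulfilled.
- **One-patient criterion.** One of six is enough, but the rise above 3-fold must come with raised bilirubin, INR or PT, jaundice, or symptoms suggesting drug-induced liver injury.
- **Catch-all.** "Other findings (regardless of the incidence rates) that at the joint discretion of the Sponsor and the Investigator" may justify halting dosing.

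Elsewhere, Section 2.3 says: "Defined stopping criteria are proposed for dosing of individual study participants, cohorts and arms". Section 4.1.4 says that "in the event of a dose-limiting adverse event (DLAE), the Investigator will contact the Sponsor immediately to discuss participant status" and the action taken or to be taken. Section 8.3.6 lists a confirmed value "or > 8x baseline (in CHB patients") among the events to be reported within 24 hours. Section 7.1 lists reasons for mandatory discontinuation. One is meeting the 4.1.3 stopping criteria, and another is "Any medical condition that the Investigator or Sponsor determines may jeopardize" the participant's safety.

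**The concern.** The fixed individual rule ends where the elevation becomes more serious. A patient confirmed at 8-fold must have the next dose delayed. A patient first confirmed at 10-fold, with normal liver function and no symptoms, falls under no sentence that says the next dose is withheld, unless a second active patient in the arm is also above 8-fold. Whether to re-dose is then a matter of judgement.

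This is a first-in-human study with repeat dosing, and Section 4.1.3 itself recognises isolated transaminase rises as a class effect. With no rule there is also no stated condition for resuming. One site could restart at 5-fold or below, as for the milder band, while another discontinues for good.

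**Working it through.** The plan states no operating characteristic for the liver rules, so there is no figure of its own to reproduce. The check is one of coverage, followed by the size of the exposed range.

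**1. Coverage.** Take one active patient with a confirmed rise, preserved liver function and no symptoms, and apply the three Part 2 liver rules of 4.1.3.

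| First confirmed value (x baseline) | Individual delay (> 5 and <= 8) | Two-of-six (> 8) | One-of-six (> 3 plus another sign) |
|---|---|---|---|
| 5.1 | yes | no | no |
| 8 | yes | no | no |
| 8.01 | no | no (1 < 2) | no |
| 10 | no | no (1 < 2) | no |
| 20 | no | no (1 < 2) | no |

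The Grade 3 or 4 laboratory criterion under the other stopping criteria also needs two of six.

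**2. Other sections.**
- 7.1, stopping-criteria entry: mandatory, but it refers to 4.1.3, where the isolated criterion is unmet with one patient.
- 7.1, liver sentence: discontinuation is to be considered for the conditions in Appendix 3, Section 6. All four combine a rise above 3-fold with bilirubin, jaundice, INR/PT or symptoms.
- 7.1, safety-jeopardy and best-interest entries, and the 4.1.3 catch-all: judgement, with no ALT threshold.
- 6.6: Investigator opinion, applied to a cohort or arm, with no ALT threshold.
- 4.1.4 and 8.3.6: contact and reporting, with no hold.

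**3. What the range means in x ULN.** Inclusion criterion 5a allows screening ALT and AST up to 2 x ULN. The band runs from 5 x b to 8 x b for baseline b.
- b = 0.5: 2.5 to 4; no explicit hold above 4.
- b = 1: 5 to 8; no explicit hold above 8.
- b = 2: 10 to 16; no explicit hold above 16.

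**4. Can a first confirmed value skip the band?** From exactly 5-fold, the next test must be more than 8/5 = 1.6 times higher; from baseline, more than 8 times. Chemistry is scheduled on Days 1, 2, 8, 15, 22 and 29 (Table 3). The gaps after Day 2 are 8 - 2 = 6 days, then 7 days. In Part 2b it follows on Days 43, 57 and 71 (Table 5), at gaps of 14 days. Skipping the band is possible; how likely it is, the documents do not say.

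**5. Doses still due.** Regimens are redacted. Assume doses fall where Tables 4 and 6 list 2-hour PK samples, and that the Day 8 dose, if there is one, is given before the confirmatory retest.

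| PK schedule | Doses, 5-week table | Left after Day 8 | Added in Table 6 | Left over 12 weeks |
|---|---|---|---|---|
| First | Days 1, 8, 15, 22, 29 | 3 | 7 (Days 36, 43, 50, 57, 64, 71, 78) | 3 + 7 = 10 |
| Second | Days 1, 15, 29 | 2 | 3 (Days 43, 57, 71) | 2 + 3 = 5 |
| Third | Days 1, 29 | 1 | 1 (Day 57) | 1 + 1 = 2 |

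**6. How often two-of-six would catch it (illustration only).** Assume independent patients with the same probability p of a confirmed isolated value above 8-fold. Among arms with at least one such patient, the share with exactly one is 6p(1 - p)^5 / [1 - (1 - p)^6]. At p = 0.10 this is 0.354 / 0.469 = 76%. At p = 0.02, 0.05, 0.20 and 0.30 it is 95%, 88%, 53% and 34%. These rates are assumptions. The shares also include patients already held in the 5- to 8-fold band, so they are an upper guide to the gap.

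**The case against.** The strongest reply is that the plan already stops such a patient. Section 7.1 is written per participant and is mandatory, Section 2.3 promises individual stopping criteria, and no single participant can experience a two-of-six event. On that reading the ladder is coherent: delay at 5- to 8-fold, discontinue above 8-fold, pause the arm at two of six. This stands as evidence of intent. It does not settle the text, because the criterion that 7.1 points to still requires two patients.

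Second, a reader might infer that oversight is lighter for the worse value. The documents do not support that. Only the value above 8-fold is labelled dose-limiting, triggers immediate Sponsor contact and is reportable within 24 hours; the milder band carries none of these. What is missing is one automatic hold.

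Third, a reader might infer that a patient already held at, say, 7-fold is released on rising above 8-fold. That is not so, because dosing resumes only at 5-fold or below. The gap concerns first confirmed values only, and isolated ones only.

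**Conclusion.** The gap is real on the text and worth fixing. In Part 2, one patient whose first confirmed isolated ALT or AST is above 8-fold baseline, with preserved liver function and no symptoms, meets no explicit individual hold, while a patient at 5- to 8-fold does.

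It would be too strong to say that the protocol directs or permits continued dosing at that level. The discretionary routes and immediate Sponsor contact are in place, and the likely intent is that dosing stops. Harm would require the Investigator and the Sponsor, both alerted, to re-dose.

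The coverage finding needs no assumption. The later-dose counts (up to 3, 2 or 1; up to 10, 5 or 2) depend on reading the dosing days from the PK columns. Counting the Day 8 dose as well would overstate the first schedule, since confirmation would normally come after that dose. No event frequency is claimed.

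**What to change.** In the 4.1.3 delay paragraph, delete the 8-fold upper limit, so that dosing of any individual participant is held for any confirmed ALT or AST above 5-fold baseline with preserved liver function. Add that, after a confirmed value above 8-fold, dosing resumes only at 5-fold or below and after review by the Investigator and the Medical Monitor. State that the stopping-criteria entry in 7.1 is to be read consistently with this. Leave the two-of-six arm pause unchanged. Writing the rule for any participant also lets the blinded site act on the laboratory value alone.

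The change is to protocol wording, with no added assessments. The cost is an occasional missed dose and lost PK/PD data in a patient with a large isolated flare, one of about six active patients in the arm. Some flares may, as the protocol notes hypothetically, reflect immune restoration. If treatment is discontinued, 7.1 allows replacement, so an extra patient is possible.

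A stricter rule, with no resumption unless a drug relation is excluded, is not needed to close the gap. With a recognised transaminase class effect it could often mean permanent discontinuation, which is a debatable trade-off.

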6.6 DOSAGE MODIFICATION

The decision to proceed to the next dose level of RO7239958 (either an increase or a decrease), will be made by the Study Team (and the Investigator) based on safety, tolerability and available PK and/or PD data obtained described as in Section 4.1.2.

If unacceptable adverse events, or pharmacological effects, reasonably attributable to RO7239958 in the opinion of the Investigator are observed in the participants in a cohort or an arm, dosing and any dose-escalation will be temporarily halted for maximally 3 weeks (see Section 4.1.2) and no further participants will be dosed until a full safety review of the study has taken place. Relevant reporting and discussion with the Medical Monitor, relevant site personnel (i.e., Investigator), and the IRB/IEC will take place before resumption of dosing.

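### In Part 2, one patient with a confirmed isolated ALT/AST rise above 5-fold and up to 8-fold baseline must be held, but one whose first confirmed value is above 8-fold has no mandatory dosing action

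*Combined protocol and SAP*

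**What the plan says.** Section 4.1.3 has three liver rules for Part 2.

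- **Participant-level delay.** "Repeat dosing of a participant within an arm will be delayed if the participant receiving RO7239958 experiences an ALT or AST increase > 5-fold" baseline. The sentence sets an upper limit of 8-fold, asks for confirmation within 48 hours, and requires bilirubin and INR or PT to be preserved. Dosing may restart at 5-fold or lower.
- **Count rule for isolated rises.** "At least two of six patients receiving RO7239958 experience a DLAE of an ALT or AST increase of > 8-fold" baseline, again confirmed and with liver function preserved. When it is met, dosing in the patient and the arm, and any escalation, is paused.
- **One-patient rule.** One of six is enough if a confirmed rise above 3-fold comes with raised bilirubin, INR or PT, with jaundice, or with symptoms pointing to drug-induced injury.

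The mandatory discontinuation list in Section 7.1 includes "If stopping criteria are met (see Section 4.1.3" and gives no ALT or AST threshold of its own. Section 2.3 describes the intended reach of the rules: "Defined stopping criteria are proposed for dosing of individual study participants, cohorts and arms".

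**The concern.** Section 4.1.3 itself names isolated transaminase rises as a recognised effect of the drug class, and this is the first study of the compound in humans. For such a risk, one expects the required action on an individual to stay the same or tighten as the rise grows. Here it is fixed up to 8-fold and then lapses. As written, a lone patient at 6-fold must miss the next dose, while a lone patient at 10-fold can receive it without a protocol deviation. Part 2a allows up to five doses over 4 weeks, so a next-dose decision can be real.

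**Working it through.** The protocol gives no operating characteristics for its stopping rules, so there is no figure to reproduce. The check is textual.

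**Step 1: the rules side by side, for one affected patient in an arm.**

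| Confirmed ALT or AST relative to baseline | Bilirubin, INR, PT, symptoms | Dosing action required by Section 4.1.3 |
|---|---|---|
| >3-fold | any abnormal, or jaundice or symptoms | pause patient, arm and escalation |
| >5-fold to 8-fold | normal, no symptoms | delay until 5-fold or lower |
| >8-fold | normal, no symptoms | none until a second of six is affected |

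**Step 2: does another provision close the third row?**

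- Section 4.1.3, other stopping criteria: Grade 3 or 4 laboratory abnormalities also need two of six. The last item, "Other findings (regardless of the incidence rates) that at the joint discretion of the Sponsor and the Investigator", can be triggered by one patient but depends on judgement.
- Section 4.1.4: "in the event of a dose-limiting adverse event (DLAE), the Investigator will contact the Sponsor immediately to discuss participant status" and action. Contact is mandatory; no action is prescribed.
- Section 6.6: "dosing and any dose-escalation will be temporarily halted for maximally 3 weeks", but only for events the Investigator finds unacceptable and attributable. There is no laboratory threshold.
- Section 7.1: stopping is mandatory once the Investigator or Sponsor sees a safety risk, so judgement comes first. Its liver sentence asks only that discontinuation be considered, for the conditions in Appendix 3, Section 6. Those are all combined findings.
- Section 8.3.6 lists "Confirmed ALT or AST > 5x ULN (in healthy participants) or > 8x baseline (in CHB patients" for reporting within 24 hours, with no dosing consequence.
- Appendix 4 provides for local results when central ones are late for a dosing decision. That implies review before dosing but sets no limit.
- Section 7.1.1 disallows temporary interruption. Its examples are logistical, but it shows that there is no general permission to pause to fall back on.

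None of these mandates a hold.

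**Step 3: how narrow is the open case?** A patient already held in the 5- to 8-fold band stays held if the value climbs, because restart requires 5-fold or lower. A patient who falls back into the band before the next dose is caught by the existing rule. What remains is a first confirmed value above 8-fold, isolated and without symptoms, still above 8-fold when a dose is due, with no second case yet confirmed in the arm.

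**Step 4: what 8-fold means.** Section 5.1 admits ALT and AST up to 2x ULN. At that limit the line is 8 x 2 = 16x ULN; at an assumed baseline of 1x or 0.5x ULN it is 8x or 4x ULN.

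**Step 5: how a count differs from a one-patient trigger (illustration only).** Let p be an assumed per-patient risk of a confirmed isolated rise above 8-fold, with six patients on active treatment. P(exactly one) = 6p(1-p)^5.

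| Assumed p | At least one of six | At least two of six | Exactly one |
|---|---|---|---|
| 5% | 26.5% | 3.3% | 23.2% |
| 10% | 46.9% | 11.4% | 35.4% |
| 20% | 73.8% | 34.5% | 39.3% |

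The last column does not estimate the open case. It is too high where rises are first caught in the 5- to 8-fold band or come after the last dose. It is too low where two patients are affected, because the first is uncovered until the second is confirmed. Section 5.5 also allows up to two extra patients per arm.

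**The case against.** The strongest reply is that the scheme is tiered: delay from 5- to 8-fold, stop above 8-fold, with the cap marking where stopping takes over. The Part 2 lead-in speaks of pausing dosing in a patient as well as in an arm, Section 7.1 is worded per participant, and Section 2.3 promises criteria for individuals. This may well be what the authors meant. It does not change the written criterion, which is a count of two of six, and no sentence gives a one-patient version. Nor can a blinded Investigator (Section 6.3.2) count actively treated patients.

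Four stronger readings are tempting, and the documents do not support them.

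- *The patient is unprotected.* Not so, given the contact, reporting and discretionary provisions in Sections 4.1.3, 4.1.4, 6.6, 7.1 and 8.3.6.
- *In Part 2b, dosing outruns chemistry, so the gap is likely there.* After Day 29, Table 5 has chemistry on Days 43, 57 and 71, and one PK column in Table 6 has weekly predose samples. But the regimens are redacted and there are three columns. The second has predose samples on exactly those three days and the third on Day 57 only. Part 2b is also optional.
- *A given percentage of arms will be affected.* Any such figure needs a rate of rises and a speed of rise, and the documents give neither.
- *One such patient should be stopped permanently.* Section 4.1.3 says the criteria were built to allow for class-effect rises and possible immune flares. An automatic permanent stop whenever a relation cannot be excluded would remove that judgement and is not needed to close the gap.

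**Conclusion.** The gap is real as written and narrow. One patient with a confirmed isolated rise above 5-fold and up to 8-fold must be held; one whose first confirmed isolated rise is above 8-fold, without symptoms, has no mandatory dosing action. The conclusion rests on the text of Section 4.1.3 and on the absence of a binding backstop elsewhere, not on a calculation. Its frequency cannot be sized from the documents. It should be corrected because it concerns a named class risk and costs little; the reporting and discretionary provisions keep it from being more serious than that.

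**What to change.** Replace the delay rule in Section 4.1.3, Part 2, with wording such as:

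> Any participant, whatever the assigned treatment, whose confirmed ALT or AST is more than 5 times baseline with bilirubin and INR or PT preserved is given no further dose until the value is back to 5 times baseline or lower. If the confirmed value exceeded 8 times baseline, dosing restarts only if the Investigator and the Medical Monitor have also completed a joint causality review that supports it.

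This deletes the 8-fold upper bound. The second sentence is needed because deletion alone would let a patient above 8-fold restart on the laboratory value only. Addressing every participant lets blinded sites apply the rule. Keep the two-of-six rule for the arm, and leave permanent discontinuation to the review. An optional cross-reference in Section 7.1.1 would prevent its ban on interruption from being read against the hold.

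The cost is a short text change with no new visits or tests, and a few more held or delayed doses, with some loss of exposure data in small arms. Section 7.1 allows replacement of participants who discontinue treatment; Section 7.2 does not allow it for those who leave the study for safety reasons.
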